***Follow-up deviations***

---

1. Missing visit or samples of QTc at 24h or ALT/AST at day 14	Minor/Major	Minor if a participant gives ALT/AST until the day 30 visit
--	-------------	---

## **6. Statistical Methods**

### **6.1. Primary safety analysis**

The main objective about the difference in QTc between the two arms 24 hours after treatment administration will be assessed by calculating the 95% confidence interval for the difference.

Non-inferiority is established if the upper limit of a one-sided 95% confidence interval around the difference in means QTc 24 hours after treatment administration (BE-PEP - SDR-PEP) is below the non-inferiority limit of +10 ms.

Analysis of covariance (ANCOVA) or an equivalent regression model correcting for the baseline values of QTc will also be used to assess the primary objective. Alternatively, the individual difference scores will be calculated by subtracting the QTc values at baseline from the ones at day 1. The difference scores will be compared using a two-sample t-test.

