4.3 Sample size

The sample size for the phase 2 trial is based on non-inferiority of the BE-PEP regimen compared to the SDR-PEP regimen in terms of adverse events, in particular QTc prolongation. We assume that in the SDR group the mean QTc will be equal to that of a reference population, i.e. 384 ms (SD 20 ms) based on the Fridericia correction method. [29]

The sample size calculations were performed by simulation, in a scenario where there is truly no difference between the standard and experimental treatment. A sample size of 64 patients are required per arm to achieve 80% power in the comparison that the upper limit of a one-sided 95% confidence interval will be below the non-inferiority limit of +10 ms.

For this part of the trial we have selected a village with a total recorded population of 908, 51% of whom are aged 18 years or above. As explained in chapter 4.2 above, as a matter of precaution we will first enroll adults and preliminarily assess their outcomes before we will start enrolling minors. The numbers of adults to be enrolled will be proportional to the observed age distribution at the time of the 2022 survey. To arrive at an accurate estimate of mean QTc for adults as well as for minors, we will recruit 150 participants per study arm, approximately 75 adults and 75 minors.

Overall, all ages combined, our intended sample size of 150 in each arm, which will provide 99% power to show that the upper limit of a one-sided 95% confidence interval will be below the non-inferiority limit of +10ms, assuming that in the larger population QTc does not differ between those receiving SDR-PEP and those receiving BE-PEP. Sample size calculations were done in R version 4.0.2.[30]

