## 3. Study outcomes and variables of interest

### 3.1. Study outcomes

#### 3.1.1. *Primary outcomes*

- Mean difference in QTc interval between the two arms 24 hours after treatment administration.
- Predetermined study stopping criteria, which will trigger an immediate pause on enrollment:
  1. Death of a participant considered related to study drug
  2. One or more participants experience an SAE or Gr 4 AE or a persistent (upon repeat testing) Gr 4 laboratory abnormality that is determined to be related to study drug
  3. Three or more participants experience a Gr 3 or greater AE of the same type (as per medical judgement) that is determined to be related to study drug
  4. Three or more participants experience a persistent (upon repeat testing) Gr 3 laboratory abnormality related to the same laboratory parameter and considered to be related to study drug
  5. Two or more participants experience QTc > 500 ms
  6. One or more participants has AST or ALT > 8x ULN, in absence of causative explanation

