### **6.5. Other aspects**

#### ***6.5.1. Subgroup analyses***

Since this is a stratified randomized trial, all analyses will be done by age-group.

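### The +10 ms QTc rule is applied to the unadjusted 24-hour difference, and the roles of the planned ANCOVA and change-score analyses are not stated

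*SAP*

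**What the plan says.** The primary outcome in SAP 3.1.1 is "Mean difference in QTc interval between the two arms 24 hours after treatment administration". SAP 6.1 builds the decision on it: "Non-inferiority is established if the upper limit of a one-sided 95% confidence interval around the difference in means QTc 24 hours after treatment administration" (BE-PEP minus SDR-PEP) "is below the non-inferiority limit of +10 ms". Protocol 9.2.1 agrees, naming a plain two-sample t-test on QTc at 24 hours.

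SAP 6.1 then adds: "Analysis of covariance (ANCOVA) or an equivalent regression model correcting for the baseline values of QTc will also be used" for the same objective. Only baseline QTc is named as a covariate. A t-test on individual changes from baseline follows as an alternative, with no criterion for choosing it.

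Three other provisions bear on this:

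- Baseline QTc is measured within a week before dosing in everyone who is dosed, because it is an eligibility criterion (protocol 4.2 and 7.2.1).
- Randomisation is stratified into three age groups (protocol 4.4, SAP 2.1).
- SAP 6.5.1 states: "Since this is a stratified randomized trial, all analyses will be done by age-group".

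**The concern.** The deciding analysis leaves out both variables that the design makes available for adjustment: baseline QTc and age stratum. With a positive correlation between baseline and day-1 QTc, a baseline-adjusted comparison estimates the same mean difference with a smaller standard error.

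The SAP also directs three analyses at one objective without ranking them. The rule names the raw difference, but the SAP does not call the other two supportive or say what follows if an adjusted limit falls on the other side of +10 ms. At stake are the width of the interval that the monitoring board will read, the precision of the age-group estimates, and clarity about which number is the trial's answer.

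**Working it through.** **Inputs.** Protocol 4.3 gives a margin of +10 ms, mean QTc "384 ms (SD 20 ms) based on the Fridericia correction method", a true difference of 0, 150 per arm, and roughly 75 adults and 75 minors per arm. The level is a one-sided 95% limit: "the upper limit of a one-sided 95% confidence interval will be below the non-inferiority limit of +10 ms". The correlation ρ between baseline and day-1 QTc is not in the documents, so I take 0.3, 0.5 and 0.7, with equal SD at both times. A true difference of 5 ms is also my assumption.

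**The plan's own figures.** The SE of the raw difference at 150 per arm is 20 × √(2/150) = 2.31 ms. Power at zero difference is Φ(10/2.31 − 1.645) = 99.6% at one-sided 0.05, or 99.1% at one-sided 0.025. The stated 99% reproduces on the raw SD, that is, for the unadjusted comparison.

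The stated 64 per arm for 80% power reproduces only at one-sided 0.025: 2 × 20² × (1.960 + 0.842)²/10² = 62.8, so 63, or 64 with the t distribution. At one-sided 0.05 the requirement is 50, or 51 with t. That is a separate point about the confidence level, but the same SAP paragraph should settle it.

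**Formulas.**

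- ANCOVA variance = raw variance × (1 − ρ²), so the reduction is ρ²: 9%, 25% and 49%.
- Change-score variance = raw variance × 2(1 − ρ): factors 1.4, 1.0 and 0.6. It is less precise than the raw difference whenever ρ is below 0.5.
- Power = Φ((10 − d)/SE − 1.645), where d is the true difference.

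| Analysis | SE, 150 per arm (ms) | Upper limit lies above estimate by 1.645 × SE (ms) | Power, 150 per arm, d = 0 | Power, 150 per arm, d = 5 | Power, 75 per arm, d = 0 |
|---|---|---|---|---|---|
| Raw | 2.31 | 3.80 | 99.6% | 70% | 92% |
| ANCOVA, ρ = 0.3 | 2.20 | 3.62 | 99.8% | 73% | 94% |
| ANCOVA, ρ = 0.5 | 2.00 | 3.29 | >99.9% | 80% | 97% |
| ANCOVA, ρ = 0.7 | 1.65 | 2.71 | >99.9% | 92% | 99.6% |
| Change, ρ = 0.3 | 2.73 | 4.49 | 98% | 57% | 83% |
| Change, ρ = 0.5 | 2.31 | 3.80 | 99.6% | 70% | 92% |
| Change, ρ = 0.7 | 1.79 | 2.94 | >99.9% | 87% | 99% |

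The 75-per-arm column approximates the adult stratum. The two strata of minors will be smaller, but their sizes are not given. Any further gain from including age stratum is not counted.

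**How often the raw and ANCOVA verdicts differ** (simulation, 150 per arm, 8,000 runs): in about 0.3-0.4% of trials at a true difference of 0, and in 16% (ρ = 0.5) to 28% (ρ = 0.8) at 5 ms.

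**The case against.** The strongest reply is that the SAP is not ambiguous about its rule. One estimate is tied to +10 ms, it matches the stated outcome and the protocol's test, and its error rate is correct: in simulation at a true difference of 10 ms it declared non-inferiority in about 5% of trials. A wider limit makes a safety claim harder to reach, so the raw rule errs on the cautious side. Under the planning assumptions power is above 99% and the verdicts almost never differ. All of this stands, and it limits the point to efficiency and clarity.

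Three stronger readings are tempting, and the documents do not support them.

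- *The baseline data go unused.* They do not. SAP 6.1 commits to running the ANCOVA; the adjustment is missing only from the decision rule.
- *Three routes allow the favourable one to be picked.* If any of the three could declare non-inferiority, the false-positive rate at a true 10 ms would be about 9-10% instead of 5% (simulation, ρ from 0.5 to 0.8). But the rule names only the raw difference. That figure shows why the roles should be labelled; it is not the plan's error rate.
- *Enrolment of children turns on this choice.* Protocol 4.2 and 4.4 make the move to younger groups depend on review of QTc measurements and adverse events. Protocol section 8 leaves the clinical relevance of any prolongation to the monitoring board. No within-stratum test against +10 ms is powered or made a condition.

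**Conclusion.** The point holds as a modest improvement. The deciding analysis is the unadjusted one, the planned ANCOVA omits age stratum, and the SAP does not say what role the two additional analyses play.

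The size rests on ρ. At 0.3 the gain is small (SE 2.31 to 2.20 ms). At 0.5-0.7 the SE falls to 2.00-1.65 ms. Overall power at zero difference has almost no room to improve. The benefit lies in the interval shown to the monitoring board, in the age-group estimates, and in the case of a true effect above zero, for which 5 ms is only an illustration. The power figures at 75 per arm measure precision; they do not describe a planned test. The conclusion that the change score is the weakest choice when ρ is below 0.5 assumes equal SDs at the two times.

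**What to change.** In SAP 6.1, and in protocol 9.2.1 so that the two documents agree:

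1. Apply the +10 ms rule to the one-sided 95% upper limit of the treatment effect from a single ANCOVA with treatment, baseline QTc and age stratum.
2. For the age-group estimates under SAP 6.5.1, use ANCOVA with treatment and baseline QTc within each stratum.
3. Report the unadjusted difference as supportive. Label the change-score comparison as a sensitivity analysis, or drop it; either is acceptable.
4. State that the supportive and sensitivity results do not decide non-inferiority.

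The quantity estimated and the margin stay as they are. The cost is one paragraph in the SAP and one sentence in the protocol, with no new data and no change to any dose or clinical rule. The change must be made before the data are analysed.

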### **6.2. Secondary safety analysis**

#### **Baseline measurements**

Data from all screened patients with QTc, ALT or AST results will be used to determine the baseline distribution of the underlying population. Data will be described both visually and by using standard summary statistics for the whole population and by demographic characteristics, such as age (same age categories as the ones used for stratified randomization) and sex. The proportion of study participants with ALT/AST values above the normal range ( $> 3$  ULN) will be calculated together with 95% Wilson confidence intervals. The proportion of study participants with QTc values above the normal range ( $> 450$  ms) will be calculated together with 95% Wilson confidence intervals.

#### **Post PEP measurements**

ALT/AST results after study drug administration (day 14 and 30) will be described both numerically and as proportions above the normal range ( $> 3$  ULN) using 95% Wilson confidence intervals pooled and by study arm. Chi-square or Fisher's exact test will be used to compare the proportions between the two study arms. The difference of the days 14 and 30 ALT/AST result with the results at baseline will be tabulated broken into categories ( $<0$ , 0-9, 10-19, etc).

The individual differences between baseline QTc and ALT/AST results and results from day 1 (QTc) or day 14 (ALT/AST) will be calculated. The difference will be described in 20ms categories ( $<0$ , 0-19, 20-39, 40-59 etc.) for QTc and in 10 U/L categories ( $<0$ , 0-9, 10-19, etc) for ALT and AST. Analysis of covariance (ANCOVA) or an equivalent regression model correcting for the baseline values of ALT/AST will be used similar to the methodology described for the primary objective. Alternatively, the individual difference scores will be calculated by subtracting the ALT/AST values at baseline from the ones at day 14 or 30. The difference scores will be compared using a two-sample t-test.

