5. STUDY PROCEDURES

5.1 General Study Procedures

The study has been planned in two phases. The main, phase 3 study will be preceded by a phase 2 study in the village of Gégé on Anjouan. In this village we will conduct door-to-door screening for leprosy in May, 2022, coinciding with the final screening round of the PEOPLE study. We will then ask for informed consent for inclusion in the phase 2 study of BE-PEOPLE. To those who consent we will provide post exposure prophylaxis with BE-PEP or SDR-PEP with intensified safety monitoring, as was described in chapter 4.4 above. Safety monitoring will include an ECG taken less than 1 week before treatment and approximately 24 hours after treatment, as well as liver function tests less than 1 week before and 14 days after treatment. In case of an ALT/AST elevation adverse event on visit D14 or absolute AST/ALT value increase of ≥ 35 between the prerecruitment visit and visit D14, liver function tests will also be included on visit D30. The team, including a medical doctor will be present during the PEP administration round (=D0), as well as the day after (=D1) to collect safety data (including QTc). The team, again including a medical doctor, will investigate the participant at the study center 14 days after (=D14) to collect additional safety data (ALT + AST) and to follow up on any ongoing (S)AE's. In case any SAE's are ongoing during the visit on D14 additional visits will be organized to follow up. A final visit to collect adverse events will be organized on D30 at the participant's house. In case liver function tests are necessary on visit D30, the participant will be invited to the study house for visit D30.

In case of any serious adverse events, transport to the hospital in the island capital Mutsamudu will be ensured, where cardiological care is provided including monitoring, electrolyte correction, and cardiac resuscitation. A project vehicle will be on standby in the village for this purpose. The results of this phase 2 safety study will be presented to the data safety monitoring board (DSMB), involved ethical committees, and local regulatory authority who will provide an opinion on whether or not the green light can be given for the main phase 3 study.

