1 Medical history deemed medically relevant for the study will be collected before signing informed consent to participate in the phase 2 trial.

2 All PEP treatment will be delivered by the health worker and intake will be directly observed.

3 Concomitant medication should be recorded from 3 weeks before D0 (day of IP administration) until 3 weeks after IP administration. After that concomitant medication should only be reported if given for an SAE.

4 In case of an ALT/AST elevation adverse events on visit day 14 or absolute AST/ALT value increase of ≥ 35 between the prerecruitment visit and visit day 14, liver function tests will also be included on visit day 30. In this case the participant will be invited to the study house to conduct visit D30.

TABLE 3: SCHEDULE OF ASSESSMENTS PHASE 3

	Screening Y1 – Y4	PEP zone Y1 – Y3	PEP 1st dose Y1 – Y3	Safety FU Day 1 Y1 – Y3	PEP 2nd dose BE-PEP⁶ Y1 – Y3	Safety FU 2nd dose Day 1 Y1 – Y3
Timing (window)	- V1 - V2: V1+365 (+-90) - V3: V2+365 (+-90) - V4: V3+365 (+-90)	- V1+25 (+-25) ⁹ - V2+25 (+-25) ⁹ - V3+25 (+-25) ⁹	- D0:V1+30 (+-30) ¹⁰ - D1:V2+30 (+-30) ¹⁰ - D2:V3+30 (+-30) ¹⁰	- D0 +1 (+3) - D1 +1 (+3) - D2 +1 (+3)	- D0*: D0 + 30 (+-7) - D1*: D1 + 30 (+-7) - D2*: D1 + 30 (+-7)	- D0* +1 (+3) - D1* +1 (+3) - D2* +1 (+3)
Enrolment participant¹	X		X ⁷			
Informed Consent	X ²		X ⁷			
Leprosy & TB physical examination	X		X ⁷			
Eligibility based on PEP zone³		X				
PEP Eligibility based on PEP Inclusion/exclusion criteria			X		X	
IP Administration^{4,5}			X		X	
Adverse Event collection			X	X	X	X
Leprosy and/or TB sampling⁸	(X)		(X)			

- 1 Every year new household members/household can be added to the study population
- 2 For new BE-PEOPLE villages (not included in the PEOPLE study) a baseline screening ICF is collected during the first screening visit. For villages enrolled in the PEOPLE study, informed consent was collected in this study to collect data and to share data with future research such as the BE-PEOPLE study.
- 3 PEP zone: Anyone living within a 100 meter radius of an index case or to the entire village if more than 50% of the population lives within a 100 meter radius of an index case
- 4 Conditional on Leprosy & TB physical examination, PEP inclusion and exclusion criteria and exposure to index cases
- 5 All PEP treatment will be delivered by the health worker and intake will be directly observed.

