For laboratory measurements see section 5.2.1. In case of ALT or AST values of $>3x$ ULN at baseline, participants will not be eligible for study medication. In case of ALT/AST elevations $>3x$ ULN after study medication, participants will undergo further ALT/AST monitoring with frequency and need for referral depending on the level of elevation.

7.2.3 (S)AE monitoring

The occurrence of any adverse events (AE) will be assessed the day after administration. An AE is any untoward medical occurrence in a clinical investigation subject administered a pharmaceutical product and which does not necessarily have a causal relationship with this product. It can be any unfavorable and unintended sign, symptom, or disease temporally associated with the use of a medicinal (investigational) product, whether or not related to this product. Participants who receive PEP will be instructed to inform the study staff of any adverse events occurring between the administration of the drug and 30 days after. All relevant study staff will be trained on (S)AE detection, (S)AE monitoring mechanisms and (S)AE reporting on site. During the training, examples of (S)AE reporting cases will be given. SAE checklists and forms will be explained as well.

In the Phase 2 study, a physician from the study team will be available in the village and a cardiologist will be on call at a nearby specialist cardiology service. In the Phase 3 study, the participants are encouraged to contact the study staff while the study teams are still in the village, or afterwards a community health officer or by using the contact details in the information form of which each household will receive a copy. For all participants provided study medication, study teams will- on arrival in the village the next day- start by visiting their houses to verify for any (S)AEs. In case the participant is not at home, another attempt will be made within the next 3 days.

For phase 2 the medical staff will specifically enquire about gastro-intestinal (nausea, vomiting, diarrhea), nervous system-related (headache, dizziness), cardiac symptoms (syncope) and cutaneous reactions. These reported adverse events will be recorded, together with their severity and relatedness to the study medication.

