## 3.2. Definitions

**QT interval:** The measured QT will be corrected by the Fridericia formula through a dedicated calculator. At baseline, QTc prolongations are defined as QTc > 450ms. Participants with a QTc value above the cut-off point will be excluded from the study. Their QTc measurement will be entered in the database and will be used in the analysis to describe the baseline QTc distribution in the population.

**Liver function measurements:** ALT and AST (U/L) will be measured at baseline (day 0) and on day 14. In both time points, participants with ALT and/or AST > 3x upper limit normal (ULN) will be considered to have abnormal (elevated) values. If a participant has an elevated ALT/AST result at recruitment, they will be excluded from the study. The ULN values for ALT and AST used for this study are 55 U/L and 48 U/L respectively (<https://www.mayoclinic.org/tests-procedures/liver-function-tests/about/pac-20394595#:~:text=Normal%20blood%20test%20results%20for,8%20to%2048%20U%2FL>). Potassium and magnesium levels will only be recorded in case of QTc prolongation,  $\geq 500$  ms at baseline or  $> 60$  ms increase as compared with baseline. Analysis of this data (potassium and magnesium results) will be purely descriptive.

Adverse events' categories and how they will be summarized are further described in section 6.3.

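### SAP 6.2 reports and tests day-30 ALT/AST by arm, although apart from a few late replacement samples only participants flagged at day 14 are re-tested then

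*SAP*

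**What the plan says.** **When ALT/AST is drawn.** Protocol 5.1 sets blood draws before dosing and at day 14. Day 30 is conditional on an ALT/AST elevation adverse event at day 14 or an "absolute AST/ALT value increase of ≥ 35 between the prerecruitment visit and visit D14, liver function tests will also be included on visit D30". Section 5.2.1 repeats the rule. So does the note to Table 2, which adds: "In this case the participant will be invited to the study house to conduct visit D30". Table 2 shows the day-30 draw in brackets. Protocol 7.2.2 provides that after a value above 3x ULN "participants will undergo further ALT/AST monitoring with frequency and need for referral depending on the level of elevation". The SAP's own definitions (3.2) list two times only: "ALT and AST (U/L) will be measured at baseline (day 0) and on day 14".

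**The other planned source of a day-30 value.** SAP Table 1 classes a missed day-14 ALT/AST as a minor deviation if a sample is given by the day-30 visit.

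**How the results are analysed.** SAP 6.2, Post PEP measurements, states that "ALT/AST results after study drug administration (day 14 and 30) will be described both numerically and as proportions above the normal range", with Wilson intervals, pooled and by arm. The next sentence compares the proportions between arms by chi-square or Fisher's test and names no day. Change from baseline is tabulated in bands for both days. Difference scores are formed by "subtracting the ALT/AST values at baseline from the ones at day 14 or 30" and go to a two-sample t-test. SAP 6.5.3 makes every specified analysis complete-case, and SAP 6.5.1 repeats all analyses by age group.

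**The concern.** A day-30 value exists mainly because the participant's own day-14 value was raised. A complete-case proportion at day 30 therefore describes people already selected for a rise, not the arm.

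The between-arm test has the same flaw. It compares two groups formed after dosing by a rule that depends on the outcome. If the regimens differ in day-14 rises, the two tested groups differ in size and make-up, and randomization no longer makes them comparable.

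Liver safety is one of the two major safety issues named in the regulator's advice annexed to the protocol. The SAP's interim analyses after each age stratum include results up to day 30. At stake is whether the day-30 liver table in that material can be read at face value.

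**Working it through.** The documents give no flag rate, expected day-30 frequency or power for this endpoint, so there is no plan figure to reproduce. The check compares the texts, then the two possible denominators.

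**1. Texts side by side**

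| Item | Protocol 5.1, 5.2.1, Table 2 | SAP 6.2 |
|---|---|---|
| Day 14 ALT/AST | everyone | proportions, arm test, changes |
| Day 30 ALT/AST | flagged participants, plus late replacements (SAP Table 1) | proportions by arm and pooled, arm test not limited to day 14, t-test on day-14 or day-30 change |
| Denominator at day 30 | – | not stated; complete-case (6.5.3), so those tested |

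Two sentences in SAP 6.2 are not clearly affected. The ANCOVA sentence names no day, and the first sentence on individual differences names day 14 only.

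**2. What the denominator does**

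Let m be the number tested at day 30 in an arm of 150, and x the number of those above 3x ULN. As written the proportion is x/m. Over all dosed it is x/150, if untested participants are taken as not elevated. The ratio is 150/m. All counts below are assumed.

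| Assumed BE-PEP x/m, SDR-PEP x/m | Tested only | All 150 per arm |
|---|---|---|
| 1/5, 1/5 | 20.0% v 20.0% (Wilson 3.6–62.4% each) | 0.7% v 0.7% (0.1–3.7% each) |
| 2/12, 1/3 | 16.7% v 33.3%, Fisher p = 0.52 | 1.3% v 0.7%, p = 1.0 |
| 4/12, 1/3 | 33.3% v 33.3%, p = 1.0 | 2.7% v 0.7%, p = 0.37 |

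In the first row the ratio is 150/5 = 30. In the second the direction of the arm difference reverses. In the third an arm difference in point estimates vanishes.

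**3. Selection effect in a simple model**

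Assumed inputs: median ALT 22 U/L, log-SD 0.40 between and 0.35 within persons, 150 per arm, flag if the day-14 rise is at least 35 U/L or the value exceeds 165 U/L. There were 4,000 simulated trials per scenario.

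- No drug effect: about 2 per arm are flagged. Their mean day-30 change is about +11 U/L, against 0 in everyone. About 20% are above 1x ULN, against 4%. In 62% of trials at least one arm has fewer than two day-30 values, so a standard two-sample t-test cannot be run.
- With a BE-PEP effect on the log scale, the mean day-30 arm difference is:

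| Effect at day 14 / day 30 | Tested only | Everyone |
|---|---|---|
| +0.3 / +0.15 | 3.1 U/L | 4.2 U/L |
| +0.3 / +0.3 | 9.6 U/L | 8.9 U/L |
| +0.5 / +0.25 | 4.5 U/L | 7.2 U/L |

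The raised day-30 level appears in every scenario. The arm difference can move either way.

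**4. Flag and reporting threshold differ**

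With the SAP's ULN values, 3x ULN is 3 × 55 = 165 U/L for ALT and 3 × 48 = 144 U/L for AST. A rise from 22 to 60 U/L is 38, so it triggers a day-30 draw while staying far below 165. In the model above, 0.6–1.5% of flagged participants exceed 165 U/L at day 14 and 0.1–0.3% at day 30, depending on scenario. Under those inputs the day-30 proportion would usually be zero, and the denominator would act through the interval: 0/2 has a Wilson upper limit of 65.8%, 0/150 one of 2.5%.

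**The case against.** **A reader might infer that the day-30 analysis would hide an excess of liver rises from the DSMB.** The documents do not support that. Day-14 ALT/AST is scheduled for everyone and reported by arm as values, proportions and banded changes. SAP 6.3 groups liver adverse events and compares arms by Fisher's test. AST or ALT above 8x ULN is a pause criterion. With an assumed 12/150 v 3/150 flagged at day 14, the flag counts themselves give Fisher p = 0.03. If 4 and 1 of them remain elevated at day 30, the all-dosed comparison gives p = 0.37, so the better denominator would not bring out a signal there either.

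**A reader might attach a fixed inflation factor to the pooled figure.** With 15 of 300 tested it would be 300/15 = 20, but that is only the ratio of assumed counts. As step 4 shows, the observed proportion may simply be zero.

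**It can be said that the SAP nowhere claims everyone is measured at day 30.** That is true: SAP 3.2 names only baseline and day 14, and SAP 6.5.3 requires missing data to be reported. But SAP 6.2 gives no denominator and no restriction, and does not mark day 30 as descriptive. A statistician following it would run the arm test on the tested subset.

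**Protocol 9.2.2 plans intervals by time point and arm for ALT/AST elevations and rules out formal comparisons between arms.** This stands. It means that moving the tests to day 14 does not by itself settle the matter.

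**The endpoint is secondary and not powered.** This also stands, and it limits the weight of the point.

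**Conclusion.** The point holds as a mismatch between the sampling rule and the analysis text. Followed literally, SAP 6.2 gives day-30 levels that do not describe the arms, and between-arm inference on a subset selected on the outcome after randomization. That conclusion needs no distributional assumption. It needs only the conditional draw, the complete-case rule and the absence of a stated denominator.

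Its size and direction cannot be derived from the documents; the figures in the working rest on assumed counts and an assumed ALT model. It would also be too strong to say that every day-30 value comes from a flagged participant, because late replacement samples make the set a mixture.

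The day-14 analyses and the primary QTc analysis are unaffected. The SAP refers to protocol version 2.1, and whether that version had the same day-30 rule cannot be checked here; the texts supplied do not match. This should be corrected before the phase 2 database lock, as a secondary safety issue.

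**What to change.** In SAP 6.2, Post PEP measurements:

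1. Remove day 30 from the between-arm proportion test, and delete *or 30* from the sentence that leads to the t-test. State that ANCOVA and change scores use day 14.
2. Report day 30 descriptively as a listing of flagged participants: baseline, day 14, day 30, resolved or not. Give the number flagged and the number tested per arm.
3. If a day-30 frequency is wanted, count anyone above 3x ULN at day 30, whether persistent or new, over all dosed participants in the arm. State the assumption that untested participants are not elevated. Counting only those elevated at both visits would miss someone flagged on a rise of 35 who first passes 3x ULN by day 30.
4. List late samples that replace a missed day-14 draw separately.
5. Reconcile any day-14 between-arm ALT/AST test that is kept with Protocol 9.2.2.

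The cost is SAP wording, plus the reconciliation in item 5. No extra visits or samples are needed.
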